5.3.5.10 Hospitalization or Prolonged Hospitalization

Any adverse event that results in hospitalization (i.e., inpatient admission to a hospital) or prolonged hospitalization should be documented and reported as a serious adverse event (per the definition of serious adverse event in Section 5.2.2), except as outlined below.

An event that leads to hospitalization under the following circumstances should not be reported as an adverse event or a serious adverse event:

- Planned hospitalization required by the protocol for breast cancer surgery
- Hospitalization for a preexisting condition, provided that all of the following criteria are met:

The hospitalization was planned prior to the study or was scheduled during the study when elective surgery became necessary because of the expected normal progression of the disease

The patient has not experienced an adverse event

An event that leads to hospitalization under the following circumstances is not considered to be a serious adverse event, but should be reported as an adverse event instead:

- Hospitalization that was necessary because of patient requirement for outpatient care outside of normal outpatient clinic operating hours

5.3.5.11 Cases of Overdose, Medication Error, Drug Abuse, or Drug Misuse

Overdose (accidental or intentional), medication error, drug abuse, and drug misuse (hereafter collectively referred to as "special situations"), are defined as follows:

- Accidental overdose: accidental administration of a drug in a quantity that is higher than the assigned dose
- Intentional overdose: intentional administration of a drug in a quantity that is higher than the assigned dose
- Medication error: accidental deviation in the administration of a drug

In some cases, a medication error may be intercepted prior to administration of the drug.

- Drug abuse: intentional excessive use of a drug that may lead to addiction or dependence, physical harm, and/or psychological harm
- Drug misuse: intentional deviation in the administration of a drug that does not qualify as drug abuse

In cases where drug is to be self-administered by the patient, drug misuse could involve the drug being administered to someone other than the patient.

Special situations are not in themselves adverse events, but may result in adverse events. Each adverse event associated with a special situation should be recorded separately on the Adverse Event eCRF. If the associated adverse event fulfills seriousness criteria, the event should be reported to the Sponsor immediately (i.e., no more than 24 hours after learning of the event; see Section 5.4.2). For GDC-9545, adverse events associated with special situations should be recorded as described below for each situation:

- Accidental overdose: Enter the adverse event term. Check the "Accidental overdose" and "Medication error" boxes.
- Intentional overdose: Enter the adverse event term. Check the "Intentional overdose" box. If drug abuse is suspected, check the "Drug abuse" box. If drug abuse is not suspected, check the "Drug misuse" box.
- Medication error that does not qualify as an overdose: Enter the adverse event term. Check the "Medication error" box.
- Medication error that qualifies as an overdose: Enter the adverse event term. Check the "Accidental overdose" and "Medication error" boxes.

- Drug abuse that does not qualify as an overdose: Enter the adverse event term. Check the "Drug abuse" box.
- Drug abuse that qualifies as an overdose: Enter the adverse event term. Check the "Intentional overdose" and "Drug abuse" boxes.
- Drug misuse that does not qualify as an overdose: Enter the adverse event term. Check the "Drug misuse" box.
- Drug misuse that qualifies as an overdose: Enter the adverse event term. Check the "Intentional overdose" and "Drug misuse" boxes.

In addition, all special situations associated with GDC-9545, regardless of whether they result in an adverse event, should be recorded on the Adverse Event eCRF as described below:

- Accidental overdose: Enter the drug name and "accidental overdose" as the event term. Check the "Accidental overdose" and "Medication error" boxes.
- Intentional overdose: Enter the drug name and "intentional overdose" as the event term. Check the "Intentional overdose" box. If drug abuse is suspected, check the "Drug abuse" box. If drug abuse is not suspected, check the "Drug misuse" box.
- Medication error that does not qualify as an overdose: Enter the name of the drug administered and a description of the error (e.g., wrong dose administered, wrong dosing schedule, incorrect route of administration, wrong drug, expired drug administered) as the event term. Check the "Medication error" box.
- Medication error that qualifies as an overdose: Enter the drug name and "accidental overdose" as the event term. Check the "Accidental overdose" and "Medication error" boxes. Enter a description of the error in the additional case details.
- Intercepted medication error: Enter the drug name and "intercepted medication error" as the event term. Check the "Medication error" box. Enter a description of the error in the additional case details.
- Drug abuse that does not qualify as an overdose: Enter the drug name and "drug abuse" as the event term. Check the "Drug abuse" box.
- Drug abuse that qualifies as an overdose: Enter the drug name and "intentional overdose" as the event term. Check the "Intentional overdose" and "Drug abuse" boxes.
- Drug misuse that does not qualify as an overdose: Enter the drug name and "drug misuse" as the event term. Check the "Drug misuse" box.
- Drug misuse that qualifies as an overdose: Enter the drug name and "intentional overdose" as the event term. Check the "Intentional overdose" and "Drug misuse" boxes.
- Drug administered to someone other than the patient: Enter the drug name and "patient supplied drug to third party" as the event term. Check the "Drug misuse" box.

As an example, an accidental overdose that resulted in a headache would require the completion of two Adverse Event eCRF pages, one to report the accidental overdose and one to report the headache. The "Accidental overdose" and "Medication error" boxes would need to be checked on both eCRF pages.

5.4 IMMEDIATE REPORTING REQUIREMENTS FROM INVESTIGATOR TO SPONSOR

Certain events require immediate reporting to allow the Sponsor to take appropriate measures to address potential new risks in a clinical trial. The investigator must report such events to the Sponsor immediately; under no circumstances should reporting take place more than 24 hours after the investigator learns of the event. The following is a list of events that the investigator must report to the Sponsor within 24 hours after learning of the event, regardless of relationship to study drug:

- Serious adverse events (defined in Section 5.2.2; see Section 5.4.2 for details on reporting requirements)
- Adverse events of special interest (defined in Section 5.2.3; see Section 5.4.2 for details on reporting requirements)

For serious adverse events and adverse events of special interest, the investigator must report new significant follow-up information for these events to the Sponsor immediately (i.e., no more than 24 hours after becoming aware of the information). New significant information includes the following:

- New signs or symptoms or a change in the diagnosis
- Significant new diagnostic test results
- Change in causality based on new information
- Change in the event's outcome, including recovery
- Additional narrative information on the clinical course of the event

Investigators must also comply with local requirements for reporting serious adverse events to the local health authority and IRB/EC.

5.4.2 Reporting Requirements for Serious Adverse Events and Adverse Events of Special Interest

5.4.2.1 Events That Occur prior to Study Drug Initiation

After informed consent has been obtained but prior to initiation of study drug, only serious adverse events caused by a protocol-mandated intervention should be reported. The paper Clinical Trial Serious Adverse Event/Adverse Event of Special Interest Reporting Form provided to investigators should be completed and submitted to the Sponsor or its designee immediately (i.e., no more than 24 hours after learning of the event), either by faxing or by scanning and emailing the form using the fax number or email address provided below:

North America: [contact]
 Email : [contact]
 [contact] (if site cannot report via fax)

EMEA and Asia Pacific: [contact]
 Email : [contact]
 [contact] (if site cannot report via fax)

5.4.2.2 Events That Occur after Study Drug Initiation

After initiation of study drug, serious adverse events and adverse events of special interest will be reported until 28 days after the final dose of study drug. Investigators should record all case details that can be gathered immediately (i.e., within 24 hours after learning of the event) on the Adverse Event eCRF and submit the report via the electronic data capture (EDC) system. A report will be generated and sent to Safety Risk Management by the EDC system.

In the event that the EDC system is unavailable, the paper Clinical Trial Serious Adverse Event/Adverse Event of Special Interest Reporting Form provided to investigators should be completed and submitted to the Sponsor or its designee immediately (i.e., no more than 24 hours after learning of the event), either by faxing or by scanning and emailing

GDC-9545—Genentech, Inc.
64/Protocol GO40987, Version 4

the form using the fax number or email address provided to investigators. Once the EDC system is available, all information will need to be entered and submitted via the EDC system.

Instructions for reporting serious adverse events that occur >28 days after the final dose of study treatment are provided in Section 5.6.

5.5 FOLLOW-UP OF PATIENTS AFTER ADVERSE EVENTS

5.5.1 Investigator Follow-Up

The investigator should follow each adverse event until the event has resolved to baseline grade or better, the event is assessed as stable by the investigator, the patient is lost to follow-up, or the patient withdraws consent. Every effort should be made to follow all serious adverse events considered to be related to study drug or trial-related procedures until a final outcome can be reported.

During the study period, resolution of adverse events (with dates) should be documented on the Adverse Event eCRF and in the patient's medical record to facilitate source data verification.

5.5.2 Sponsor Follow-Up

For serious adverse events and adverse events of special interest, the Sponsor or a designee may follow up by telephone, fax, email, and/or a monitoring visit to obtain additional case details and outcome information (e.g., from hospital discharge summaries, consultant reports, autopsy reports) in order to perform an independent medical assessment of the reported case.

5.6 ADVERSE EVENTS THAT OCCUR AFTER THE ADVERSE EVENT REPORTING PERIOD

The Sponsor should be notified if the investigator becomes aware of any serious adverse event that occurs after the end of the adverse event reporting period (defined as 28 days after the final dose of study drug), if the event is believed to be related to prior study drug treatment. These events should be reported through use of the Adverse Event eCRF. However, if the EDC system is not available, the investigator should report these events directly to the Sponsor or its designee, either by faxing or by scanning and emailing the paper Clinical Trial Serious Adverse Event/Adverse Event of Special Interest Reporting Form using the fax number or email address provided in Section 5.4.2.1.

5.7 EXPEDITED REPORTING TO HEALTH AUTHORITIES, INVESTIGATORS, INSTITUTIONAL REVIEW BOARDS, AND ETHICS COMMITTEES

The Sponsor will promptly evaluate all serious adverse events and adverse events of special interest against cumulative product experience to identify and expeditiously communicate possible new safety findings to investigators, IRBs, ECs, and applicable health authorities based on applicable legislation.

To determine reporting requirements for single adverse event cases, the Sponsor will assess the expectedness of these events using the following reference document:

- GDC-9545 Investigator's Brochure

The Sponsor will compare the severity of each event and the cumulative event frequency reported for the study with the severity and frequency reported in the applicable reference document.

Reporting requirements will also be based on the investigator's assessment of causality and seriousness, with allowance for upgrading by the Sponsor as needed.

6. STATISTICAL CONSIDERATIONS AND ANALYSIS PLAN

The final analysis will be performed after LPLV and subsequent data cleaning. The safety analysis will be based on the safety-evaluable population, and activity analysis will be based on the patients who completed study treatment. All summaries will be presented according to the assigned dose level and cohort. In general, data will be summarized as warranted, and listings will be used in place of tables when the sample sizes are small. Continuous variables will be summarized using means, standard deviations, median, and ranges; categorical variables will be summarized using counts and percentages.

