3. STUDY DESIGN

3.1 DESCRIPTION OF THE STUDY

This is a Phase I, open-label, multicenter, preoperative study to assess changes in Ki67 levels and to evaluate the pharmacodynamics, pharmacokinetics, safety, and biologic activity of GDC-9545 in postmenopausal patients with Stage I–III operable ER-positive (HER2-negative) untreated breast cancer. Approximately 75 patients are expected to be enrolled in this study, at approximately 20–30 investigative sites globally.

The study consists of a screening period of up to 28 days; a treatment period of approximately 14 days, including a day for surgery; and a minimum follow-up period of 28 days. Patients will be assigned to one of three treatment cohorts (10, 30, and 100 mg; see [Figure 1](#)). GDC-9545 will be administered once daily up to and including the day of surgery (if allowed per local process) on Day 15 (± 2 days).

All patients will be required to provide a pretreatment tumor tissue sample. Archival tumor tissue from prior diagnostic formalin-fixed, paraffin-embedded cores (FFPE) may be used; however, if archival tissue is not available or is determined to be unsuitable for required testing, the patient will undergo a tumor biopsy. For the purpose of enrollment, ER, PR, and HER2 will be locally determined prior to beginning of study treatment. Patients who are not evaluable for the primary activity analysis as defined in [Section 6](#) will be replaced.

Surgery will take place on Day 15 (± 2). If surgery must be delayed >2 days, the Medical Monitor should be consulted. Surgery should be performed within 24 hours after the last dose of GDC-9545, if possible, to best observe PD knockdown with GDC-9545 in the surgical specimen. In lieu of surgical specimen, a biopsy on Day 14 may be obtained. The surgical specimen is not required if biopsy is obtained on Day 14.

All patients will be closely monitored for adverse events throughout the study and for at least 28 days after the final dose of study treatment (see [Section 5.3.1](#)). Adverse events will be graded according to the National Cancer Institute Common Terminology Criteria for Adverse Events, Version 5.0 (NCI CTCAE v5.0). In addition to the safety assessments conducted at scheduled clinic visits, patients will be contacted for a general assessment of adverse events at 24 hours post-surgery by telephone, if applicable.

[figure not shown]

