4.3.1 Study Treatment Formulation, Packaging, and Handling

4.3.1.1 GDC-9545

GDC-9545 will be supplied by the Sponsor and will be provided in two different strengths, 10-mg and 50-mg tablets, packaged in high-density polyethylene bottles with a plastic child-resistant cap with induction seal and desiccant. For information on the formulation and handling of GDC-9545, see the pharmacy manual and the GDC-9545 Investigator's Brochure.

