6.4 SAFETY ANALYSES

For safety analyses, the analysis population will include all enrolled patients who receive at least one dose of study medication.

Study treatment discontinuation and reasons for patient discontinuations from the study will be described and summarized. Study drug administration data will be listed and any dose modifications will be flagged.

Safety will be assessed through summaries of adverse events, changes in laboratory test results (including ECGs), changes in vital signs, and GDC-9545 exposure. All adverse events occurring on or after treatment on Day 1 will be summarized by mapped term, appropriate thesaurus levels, and NCI CTCAE v5.0 toxicity grade. Relevant laboratory and vital sign (pulse rate, blood pressure, and temperature) data will be displayed by time, with NCI CTCAE v5.0 Grade 3 and 4 values identified, where appropriate. Additionally, all laboratory data will be summarized by NCI CTCAE v5.0.

Safety data will be accumulated up to the end of the patient's follow-up period.

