6.5 PHARMACOKINETIC ANALYSES

The sparse PK concentration data at the steady state will be summarized by dose level and compared with the historical PK profiles from the Phase I study.

Additional PK analyses may be conducted as appropriate.

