6.6 ACTIVITY ANALYSES

The activity analysis population will consist of all patients who completed study treatment and who have tumor biopsy specimens available at baseline and at surgery for assessment of activity.

The activity is defined as change from baseline in tumor cell proliferation measured by Ki67 expression between pre- and post-treatment samples. The activity will be summarized by dose level.

On the assumption of a log normal distribution, Ki67 values will be log transformed before analysis. $\log(\text{Ki67}_{\text{post}})$ and $\log(\text{Ki67}_{\text{pre}})$ will be used to denote the mean of the logs of the post-treatment and pre-treatment values, respectively. A value of 0.1 will be added to every untransformed Ki67 value to avoid the mathematical anomaly that arises because the log of zero is minus infinity. The result of mean log changes and CI can be calculated and displayed on their original scale by back transformation.

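### Safety and PK summaries are grouped by assigned dose without exception, so a patient on a sustained wrong dose would be tabulated under a dose she mostly did not take

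*Combined protocol and SAP*

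**What the plan says.** The general rule at the head of Section 6, repeated in the synopsis under Statistical Methods, is: "All summaries will be presented according to the assigned dose level and cohort". The later subsections do not change it:

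- **Section 6.4 (safety):** "the analysis population will include all enrolled patients who receive at least one dose of study medication". This says who is in the population, not under which dose she is shown. On departures from the planned dose, the section adds: "Study drug administration data will be listed and any dose modifications will be flagged".
- **Section 6.5 (PK):** "The sparse PK concentration data at the steady state will be summarized by dose level". It does not say whether that is the assigned or the received dose.
- **Section 6.6 (activity):** "The activity will be summarized by dose level".

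Neither Section 6 nor the synopsis has a rule for dose actually received.

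Elsewhere the protocol foresees that the two doses can differ. Drug is "provided in two different strengths, 10-mg and 50-mg tablets" (Section 4.3.1.1), and dosing after Day 1 is outpatient (Section 4.3.2). Section 5.3.5.11 defines overdose relative to the assigned dose, gives the definition "Medication error: accidental deviation in the administration of a drug", and names a wrong dose among the errors to be entered on the Adverse Event eCRF.

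**The concern.** A table of adverse events by dose is read as describing what happened at that dose. So is a table of concentrations by dose. When a patient has mostly taken something else, grouping by assignment makes both tables wrong for her. Section 5.1.2.1 rules out dose reductions, which removes planned departures, but it does not prevent dispensing or counting errors.

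Tolerability is a stated objective (Section 2.1). The one PK sample per patient is there to confirm exposure at 10, 30 and 100 mg (Section 3.3.3) and is compared with historical profiles (Section 6.5). Two of the three cohorts are small, so one patient carries visible weight. A rule fixed now also avoids having to choose a grouping after the data are seen.

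**Working it through.** The plan gives no figure on this point, so there is none to reproduce. The check has four parts.

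**1. Does any text override the general rule?** Section 6 and the synopsis apply assigned dose to all summaries. Section 6.4 tests for any exposure and sets no grouping. Sections 6.5 and 6.6 say only that results are by dose level. Section 6.2 lists and evaluates major deviations without regrouping. The assigned-dose rule therefore governs safety and PK.

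**2. Weight of one patient in an event rate.** Section 6.1 gives at least 15 patients per cohort, 45 at 30 mg, and about 75 in all. Cohorts of 15, 45 and 15 fit: 15 + 45 + 15 = 75. Let *x* of the other *n* − 1 patients in her assigned cohort have the event.

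- She has the event: the rate is (*x* + 1)/*n* with her and *x*/(*n* − 1) without her. The gap is largest at *x* = 0, where it is 1/*n*: 1/15 = 6.7 points or 1/45 = 2.2 points.
- She does not have it: only the denominator moves. For example, 2/15 = 13.3% becomes 2/14 = 14.3%, a change of 1.0 point.

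**3. Weight of one patient in a PK mean.** Assume exposure proportional to dose and a wrong dose sustained up to the sample. The documents do not state proportionality in patients; Section 1.2.2 says only that exposure rose with dose. Section 6 plans arithmetic means, so, in dose units:

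| Assigned cohort | Dose one patient took | Cohort mean | Change |
|---|---|---|---|
| 10 mg, n = 15 | 30 mg | (14×10 + 30)/15 = 11.3 | +13% |
| 10 mg, n = 15 | 100 mg | (14×10 + 100)/15 = 16.0 | +60% |
| 30 mg, n = 45 | 10 mg | (44×30 + 10)/45 = 29.6 | −1.5% |
| 30 mg, n = 45 | 100 mg | (44×30 + 100)/45 = 31.6 | +5% |
| 100 mg, n = 15 | 10 mg | (14×100 + 10)/15 = 94.0 | −6% |

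These are illustrations, not forecasts. The planned medians would move much less than the means.

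**4. Which doses decide the PK sample?** Section 1.2.2 gives single-dose half-lives of 26.2 to 41.4 hours. Assume first-order elimination with the same half-life on repeated daily dosing. The last *k* doses then supply a share 1 − 2^(−24*k*/t½) of the steady-state concentration:

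- *k* = 3: 1 − 2^(−72/26.2) = 85%, or 1 − 2^(−72/41.4) = 70%.
- *k* = 5: 1 − 2^(−120/26.2) = 96%, or 1 − 2^(−120/41.4) = 87%.

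A patient dosed correctly on Days 1 to 10 and wrongly afterwards would still pass a majority-of-days rule, although most of her measured concentration came from the wrong doses. Safety and PK therefore need different rules.

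**The case against.** The case on the other side is substantial, and much of it stands.

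- **Contradiction.** A reader might infer that a safety population defined by drug received contradicts tabulation by assigned dose. It does not. Section 6.4 asks only whether any drug was taken. This is a rule that handles one contingency badly, not an internal inconsistency.
- **Isolated errors.** A reader might infer that any wrong dose misplaces the patient. With one wrong day in about 14 she has received her assigned dose, and her safety data belong where the plan puts them. The error definitions in Section 5.3.5.11 cover single-dose and even intercepted errors, so they are not evidence of sustained misdosing.
- **Detection.** A reader might infer that a signal could be hidden. Diaries and unused drug are reviewed on Day 8 and at the surgery visit (Appendix 1). Every medication error is entered as its own event term (Section 5.3.5.11). Administration data are listed and exposure is summarised (Section 6.4). Major deviations are evaluated for their effect on interpretation (Section 6.2). The error would be visible. What remains is that none of these steps moves the patient to another column of the by-dose tables.
- **Likelihood.** A 30 mg dose cannot be made from 50-mg tablets, so with whole tablets the 10 and 30 mg doses differ only in the count of 10-mg tablets. That makes an error possible but does not show it to be likely. The dispensing instructions are in the pharmacy manual, which is not among the documents.
- **Stakes.** Section 3.3.2 assigns the traditional safety endpoints to the dose-escalation/expansion study and gives this study biomarker endpoints. No stopping or dose-selection rule in the documents uses a cohort's adverse-event rate.

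**Conclusion.** The point holds, as a small and contingent one. The plan states a grouping rule for all summaries that gives the wrong answer in two situations: for safety, when a patient takes a dose other than the assigned one for most of treatment; and for PK, when the doses leading up to the single sample were wrong.

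If neither happens, the effect is zero. The documents give no frequency, and none can be derived from them. A reader might take 6.7 points as the effect of any misdosed patient. It is an upper limit for one patient in a 15-patient cohort who has the event when no one else there does. The PK percentages rest in addition on dose-proportional exposure. Nothing here affects the sample size or the Ki67 analysis.

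**What to change.** In Section 6 and the synopsis, replace the single grouping sentence with a short rule:

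- Safety is summarised by dose actually received, defined as the dose taken on most treatment days.
- PK is summarised by the dose actually taken in the days before the sample, with the number of days fixed in advance. The half-life calculation above can guide that choice.
- A patient whose received dose matches no cohort, or whose dosing is too mixed to classify, is listed and shown separately.
- Conduct and activity summaries stay by assigned dose.
- Every patient whose assigned and received doses differ is listed.

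Sections 6.4 and 6.5 should then refer to the received dose explicitly.

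The cost is a small amount of extra programming and agreement on the mixed-dosing rule. The data are already planned: the diary and returned drug (Section 4.3.2), the administration eCRF, and the recorded dose time before the PK sample (Appendix 1). The change concerns analysis grouping only. It alters no treatment and leaves the sample size as it is.
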